4. GOALS

4.1. Main objective

To evaluate the acceptability of the cognitive stimulation program based on virtual reality among patients with mild or moderate cognitive impairment at the El Carme Socio-Health Center in Badalona.

4.2. Goals specific

To investigate whether VR interventions are perceived as useful and motivating by patients, which would translate into positive adherence to the cognitive stimulation program.

Measure changes in cognitive performance (particularly in attention and memory) of patients before and after the VR intervention to evaluate the effectiveness of the cognitive stimulation program.

Understand how healthcare professionals perceive VR interventions in terms of their applicability in the clinical practice of cognitive stimulation.

Identify possible improvements in the implementation of the VR program based on the comments and suggestions of patients and healthcare personnel.

Collect data and information that could be useful in developing future VR experiences for patients with cognitive impairment.

5. RESEARCH METHODS

5.1 Study type

Type of study: Non-randomized prospective pilot study interventionist

Study Description: This is an interventional study where an intervention not used in conventional practice will be evaluated, which consists of the use of virtual reality experiences for cognitive stimulation in patients with mild or moderate cognitive impairment. The VR experiences will be developed in collaboration with a technological partner, with the aim of potentially being incorporated into the cognitive rehabilitation program at the El Carme Socio-Health Center (CSSC) Day Hospital.

5.2 Design

This study will be prospective and non-randomized in design. Patients will be selected from among those who already attend cognitive rehabilitation sessions at the CSSC Day Hospital. There will be no control group in this pilot study, as the primary objective is to evaluate the usability and acceptability of the intervention.

Experimental group: This group will be made up of 20 patients who attend cognitive rehabilitation sessions at the CSSC Day Hospital. These patients will participate in 8 cognitive rehabilitation sessions that will incorporate the VR experiences developed for this study.

Intervention

Sessions:

The 8 sessions will be held two days a week, at the time when the included participants have an appointment for the conventional cognitive rehabilitation program at the CSSC Day Hospital.

Equipment and Technology:

We use Oculus Quest 2 glasses and their hand tracking technology, which allows for a more immersive and less complicated experience for participants, especially those with MCI.

Developed Virtual Reality Experiences:

A) Interactive Cognitive Stimulation Exercises (Declarative Memory, Executive Functions):

Developed jointly by the BSA VR and Reality Telling teams, following the researchers' guidelines, three types of sequential interactive exercises have been created:

Step 1- Make a Purchase at the Supermarket:

- Scenario: Virtual supermarket.
- Avatar: An animated avatar greets the participant and provides instructions.
- Objective: Select ingredients to make a potato omelet or gazpacho.
- Interaction: Participants use hand tracking technology to grab products and place them in a virtual cart.
- Feedback: A success or error audio is emitted based on the product selection.

Step 2- Pay for the Purchase:

- Scenario: Checkout area of the virtual supermarket.
- Avatar: An animated avatar greets the participant and provides instructions.
- Objective: Pay the exact amount for the selected products.
- Interaction: Select 3D models of bills and coins to reach the correct sum.
- Feedback: An avatar and audio provide confirmation or correction.

Step 3- Sort the Recipe Steps:

- Scenario: Virtual kitchen.
- Avatar: An animated avatar greets the participant and provides instructions.
- Objective: Sort photos of the recipe steps.
- Interaction: Drag and drop photos into a numbered panel.
- Feedback: Confirmation of the avatar.

Scenario details:

- Step 1: Make a purchase at the supermarket. Upon entering the supermarket, an animated avatar greets the participant and explains that they must select the correct products to make a potato omelet or gazpacho. The products are arranged on a shelf, there are correct products and others incorrect. Participants must select by grabbing the products with their hand and taking them to the shopping cart. When you drop the products into the cart, the program recognizes them as correct or incorrect. If it is a correct product, an event audio plays and the product stays in the cart, if it is an incorrect one, an audio plays explaining that this product is incorrect, and the object automatically returns to the shelf.
- Step 2: Pay for the purchase. In this exercise, the avatar explains that the ATM is not working and requests that they pay for the purchase with the exact value. We have created some 3D models of money and coins that are arranged next to the ATM. The value of money is added up on a screen as you select each of these models. If we go beyond the desired total, an audio plays explaining that we must try again, and the sum returns to zero. When the desired value is reached, it adds a congratulating audio.
- Step 3: Order the steps of the recipe. In a kitchen, an animated avatar explains the exercise. We have before us some photos with the steps of the recipes for a tortilla or a gazpacho, and a box with 6 numbered spaces. The goal is to sort the photos of the steps, placing each of them in the numbered box in the correct order.

B) Cognitive Stimulation with Videos (Attention and Episodic Memory):

- Description of the Videos: 360-degree videos have been recorded in known environments in Badalona to maximize the familiarity and comfort of the participants, who are mostly residents of the area. The videos are of two types: static, where the perspective does not change; and in movement, which simulates a slow walk.

- Real-time tracking technology: An application will be used that will allow the therapist to follow the video in real time on a tablet. This will facilitate the interaction between the therapist and the participant, improving the effectiveness of cognitive stimulation. - Video

Listing:

- Video 1 (6:24) "Plaça de la Vila Badalona". Static video in front of the Badalona town hall.
- Video 2 (5:00) "Carrer de Mar Badalona". Motion video walking slowly along the main pedestrian street of Badalona
- Video 3 (3:06) "Pas soterrani cap a la platja". In motion walking slowly from the end of Calle de Mar to the beach.
 - Video 4 (2:00) "Walking along the Passeig Maritim Badalona Part 1". In motion walking at the beginning of the Passeig Marítim de Badalona.
- Video 5 (2:00) "Walking along the Passeig Maritim Badalona Part 2". In motion walking along the Passeig Marítim.
- Video 6 (3:30) "Walking along the Passeig Maritim Badalona Part 3". In motion walking along the Passeig Marítim from Anis del Mono to Pont del Petroli.
- Video 7 (5:00) "You saw the Pont del Petroli Badalona". Static on a balcony with views of the sea and the Pont del Petroli.
 - Video 8 (5:00) "Badalona Coconut Beach". Static on the Passeig Marítim.
- Cognitive Stimulation Procedure with the videos:
- Method: Visual-verbal stimulation in real time carried out by a researcher who accompanies the session.
- Activity: While watching the videos, the researcher accompanying the session asks the participants to pay attention to specific elements, such as if they recognize the place, how many bicycles they have passed, if they have seen a dog, etc.
- Interrogation:

At the beginning of the session, the type of visualization to be carried out will be entered (*"Next you will watch a video of a square in which you will see different scenes. Stay tuned."*).

While viewing the scenes, you will be asked questions regarding the environment and the elements that appear to encourage attention. ("Do you recognize the square? Have you ever been? What is it called? What are you seeing? Pay close attention to all the details.").

At the end of each video, open and multiple choice questions will be asked. ("Have you seen any animals? How many dogs have you seen passing by, 2 or 5?...") to evaluate attention and memory regarding the elements shown.

- Objectives: The objective of this intervention is to stimulate and evaluate aspects of cognitive function such as attention (focused, sustained and alternating), memory and visuospatial function (immediate, working, episodic, semantic, spatial orientation, visual memory).
- Participant Feedback: At the end of the session, feedback will be collected from participants to improve future interactions of the exercise.

5.3 Participating population

Source population: The source population of the study will be the patients who attend the cognitive rehabilitation program at the Centro Sociosanitario El Carme (CSSC) in Badalona Serviceis Asistencianals.

Location: El Carme Socio-Health Center (CSSC), Badalona, Spain.

Selection period: Participants will be selected from September to October 2023.

Inclusion criteria:

- Participants must be at least 60 years old, with no maximum age limit.
- Participants must be classified as having mild cognitive impairment with an MMSE score > 23.
- Participants must be currently attending cognitive rehabilitation sessions at the CSSC Day Hospital.
- Participants must be able to give informed consent or, in the event of incapacity, consent must be obtained from their legal representative.

- Exclusion criteria

- Patients with a serious or unstable illness that may interfere with their participation in the study.
- Patients with severe psychiatric disorders, such as psychotic disorders, delusions or hallucinations that may be exacerbated by the use of virtual reality.
- Patients with severe visual limitations that would prevent the use of virtual reality.
- The presence of eye diseases that cause blurred vision that cannot be corrected with contact lenses or glasses.
- Presence of hearing pathologies that cause a significant decrease in hearing without hearing aids.
- High sensitivity to motion sickness.
- Epileptic subject.
- Patients who are unable or unwilling to give informed consent.

Withdrawal criteria

Withdrawal criteria will include the appearance of health problems that may interfere with continued participation in the study, or withdrawal of consent by the participant.

Sampling type

The type of sampling will be non-probabilistic sequential. All patients who meet the inclusion criteria and do not meet any of the exclusion criteria will be invited to participate until the desired number of participants is reached.

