5.4 Study variables

5.4.1 Variables result, exposure or effect

Main Outcome Variable:

Acceptability and usability of VR exercises: This will be measured using a user satisfaction questionnaire and the System Usability Scale (SUS). HE will managen after the last session (the eighth).

Secondary Outcome Variables:

Cognitive function (memory and attention), measured through standardized tests: - Specific to attention and memory (Digits, TMT [Annex 3], SDMT [Annex 4]).

- General cognitive function tests:
- Montreal Cognitive Assessment (MoCA) [anexo 5]
- Mini-Mental State Examination (MMSE) [anexo 6]

The evaluations will be carried out before starting the training program and at the end of it (after the eighth session).

Usability of the system by professionals:

This will be evaluated using the System Usability Scale (SUS) for patients and professionals [Annex 7 and 8]. It will be administered to professionals after completing the training program.

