5.4.2 Other variables

- Age
- Sex
- Etiology of cognitive impairment
- Schooling
- Exposure to other treatments: Any additional medication or cognitive therapy that the patient is simultaneously participating in will be recorded.

5.5 Study Evaluations:

Visit	Procedures		
Selection visit (Pre-study)	Informed consent, collection of demographic data and results of cognitive function variables		
Visit 1 (Session 1)	Starting VR training sessions		
Visit 2 (Session 8 - Final)	Completion of the VR training sessions, questionnaires on cognitive function and satisfaction and usability variables.		

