5.7 Statistical analysis

The data collected during the study will be analyzed using statistical methods appropriate for each type of variable. All analyses will be performed using statistical software SPSS 27.0.

Acceptability and Usability: Scores obtained on the System Usability Scale (SUS) will be analyzed descriptively to provide an overall measure of the acceptability and usability of the VR intervention.

Cognitive function: Depending on the normality of the variables, statistical tests will be applied to compare scores (parametric Student's T or non-parametric Wilcoxon (in the case of failure to comply with the assumption of normality).

Demographic and clinical variables: Correlation and multiple regression analyzes will be used to examine relationships between demographic and clinical variables (e.g., age, gender, etiology, education) and changes in acceptability, usability, cognitive function, and quality of life.

The hypotheses will be evaluated at the significance level of p < 0.05 (95% confidence level). As this is a pilot study, the results will be used primarily to generate hypotheses for future research and to provide effect size estimates that may be useful for sample size calculation in future studies.

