ANNEX 4. Attention and memory test: SDMT

Institut Català de la Salut

ANEXO 5. Montreal Cognitive Assessment (MoCA)

ANEXO 6. Mini-Mental State Examination (MMSE)

Mini-Mental State Examination (MMSE)

Patient's code:

Date:

Instructions: Ask the questions in the order listed. Score one point for each correct response within each question or activity.

Maximum Score	Patient's Score	Questions
5		"What is the year? Season? Date? Day of the week? Month?"
5		"Where are we now: State? County? Town/city? Hospital? Floor?"
3		The examiner names three unrelated objects clearly and slowly, then asks the patient to name all three of them. The patient's response is used for scoring. The examiner repeats them until patient learns all of them, if possible. Number of trials:
5		"I would like you to count backward from 100 by sevens." (93, 86, 79, 72, 65, …) Stop after five answers. Alternative: "Spell WORLD backwards." (D-L-R-O-W)
3		"Earlier I told you the names of three things. Can you tell me what those were?"
2		Show the patient two simple objects, such as a wristwatch and a pencil, and ask the patient to name them.
1		"Repeat the phrase: 'No ifs, ands, or buts.'"
3		"Take the paper in your right hand, fold it in half, and put it on the floor." (The examiner gives the patient a piece of blank paper.)
1		"Please read this and do what it says." (Written instruction is "Close your eyes.")
1		"Make up and write a sentence about anything." (This sentence must contain a noun and a verb.)
1		"Please copy this picture." (The examiner gives the patient a blank piece of paper and asks him/her to draw the symbol below. All 10 angles must be present and two must intersect.)
30		TOTAL

1

(Adapted from Rovner & Folstein, 1987)

Source: www.medicine.uiowa.edu/igec/tools/cognitive/MMSE.pdf Provided by NHCQF, 0106-410 Instructions for administration and scoring of the MMSE

Orientation (10 points):

- Ask for the date. Then specifically ask for parts omitted (e.g., "Can you also tell me what season it is?"). One point for each correct answer.
- Ask in turn, "Can you tell me the name of this hospital (town, county, etc.)?" One point for each correct answer.

Registration (3 points):

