- Copying: Show the patient the picture of two intersecting pentagons and ask the patient to copy the figure exactly as it is. All ten angles must be present and two must intersect to score one point. Ignore tremor and rotation.

(Folstein, Folstein & McHugh, 1975)

2

Source: www.medicine.uiowa.edu/igec/tools/cognitive/MMSE.pdf Provided by NHCQF, 0106-410 Interpretation of the MMSE

Method	Score	Interpretation
Single Cutoff	<24	Abnormal
Range	<21	Increased odds of dementia
	>25	Decreased odds of dementia
Education	21	Abnormal for 8 th grade education
	<23	Abnormal for high school education
	<24	Abnormal for college education
Severity	24-30	No cognitive impairment
	18-23	Mild cognitive impairment
	0-17	Severe cognitive impairment

Sources:

Source: www.medicine.uiowa.edu/igec/tools/cognitive/MMSE.pdf Provided by NHCQF, 0106-410

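### MMSE > 23 is an entry criterion and MMSE is also a tested before-after outcome: if the selection-visit score serves both uses, as the schedule implies, the change is pulled down, and the cap at 30 limits any gain

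*Combined protocol and SAP*

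**What the plan says.** - **Entry (5.3).** The criterion reads "Participants must be classified as having mild cognitive impairment with an MMSE score > 23". MMSE is scored in whole points and the Annex 6 item maxima sum to 30, so qualifying scores are 24 to 30.
- **Outcome (5.4.1).** MMSE and MoCA are the two general cognition tests among the secondary outcomes, given before the programme and after session 8.
- **Schedule (5.5).** The selection visit covers "Informed consent, collection of demographic data and results of cognitive function variables". The row for session 1 lists only the start of VR training. No other pre-programme cognitive assessment appears.
- **Analysis (5.2, 5.7).** There is no control group. Cognitive scores are compared by "parametric Student's T or non-parametric Wilcoxon" at p < 0.05. Section 5.7 also says that the results should supply effect sizes for sizing later studies.
- **Limitations (5.8).** The lack of a control group is listed. Selection on an outcome, regression to the mean and a ceiling are not.
- **Annex 6, severity rows.** 24-30 is labelled "No cognitive impairment" and 18-23 "Mild cognitive impairment".

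**The concern.** A score used to admit patients is a poor baseline for measuring their change. An entry floor keeps patients whose score was high by chance that day and drops those whose score was low by chance. On retest the chance part is not repeated, so the mean is expected to fall even if nobody has changed. A scale that stops at 30 adds a second problem: a patient near the top has little room to show a gain.

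Both effects work against the secondary hypothesis that cognition improves, and with no comparison arm neither can be told apart from an effect of VR. The practical stake is less the p-value from 20 patients than the point estimate, because 5.7 would pass it on to the planning of later trials.

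There is also a question of description. Read against the severity rows of Annex 6, the entry rule admits only scores labelled unimpaired and excludes every score labelled mild.

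**Working it through.** The plan gives no power calculation, SD or expected change for MMSE, so there is no planned figure to reproduce.

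**1. Range and headroom (from the documents).** Item maxima: 5+5+3+5+3+2+1+3+1+1+1 = 30. A whole-number score above 23 is 24 to 30. Room for gain is 30 minus baseline: 6, 5, 4, 3, 2, 1 or 0 points.

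**2. Pull from selection (inputs assumed).** Let the clinic's MMSE have mean μ, SD σ and test-retest reliability r. Patients enter if the first score is at least 24, that is above 23.5 before rounding. With no true change, and ignoring rounding and the cap:

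expected change = -(1 - r) × σ × λ(z), where z = (23.5 - μ)/σ and λ(z) = φ(z)/(1 - Φ(z)).

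Middle case, μ = 24, σ = 3, r = 0.8: z = -0.167, λ = 0.3934/0.5662 = 0.695, change = -0.2 × 3 × 0.695 = -0.42.

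A simulation of the same model, with scores rounded and capped at 30, was run for μ = 23 to 27, σ = 2 and 3, and r = 0.7, 0.8 and 0.9:

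| Case | Formula | Simulated |
|---|---|---|
| Smallest pull: μ 27, σ 2, r 0.9 | -0.02 | -0.02 |
| Middle: μ 24, σ 3, r 0.8 | -0.42 | -0.44 |
| Largest pull: μ 23, σ 3, r 0.7 | -0.82 | -0.84 |

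The small differences come from rounding. Wider assumptions (μ 22 to 27, σ 2.5 to 3.5) give -0.05 to -1.17, negative in all 30 cases.

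**3. A true gain of 1 point.** With one score for both uses it appears as 0.12 to 0.91 points over the grid of step 2, and as about 0.5 in the middle case.

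**4. Separate entry and baseline scores.** With no true effect the expected change returns to 0.00 in every case, and some baselines fall below 24 (2% to 31% over the grid of step 2). The cap still matters: a true gain of 1 point appears as 0.77 to 1.00. So the pull in step 2 comes from selection, and the cap acts separately by trimming real gains.

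**5. Scale against n = 20.** The 95% half-width for a mean change is 2.093/√20 = 0.468 SD of the change. The simulated SD of the change is 0.94 to 2.19, so the half-width is 0.44 to 1.03 points. The pull is smaller than the half-width in every case of the step 2 grid. In the wider grid it can exceed it: μ 22, σ 2.5, r 0.7 gives 0.95 against 0.468 × 1.86 = 0.87.

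**6. Effect on planning.** Required sample size varies with the inverse square of the effect. In the middle case, a true 1-point gain read as 0.5 would inflate a later trial's size by about (1/0.5)² = 4, with the SD held fixed.

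**The case against.** **One score for both uses is not stated.** This is the strongest objection, and it stands. Section 5.4.1 says only that testing precedes training. Section 6.1 takes the degree of impairment partly from medical records, 5.3 recruits patients already in the rehabilitation programme, and section 11 puts recruitment in September-October 2023 and the start of data collection in November. Entry could rest on a chart score with a fresh MMSE before session 1. The pull would then vanish. A reader might infer that every patient starts at 24 to 30; the documents do not establish that.

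**The net direction is unknown.** A reader might infer that MMSE must show no improvement whatever VR does. That does not follow. The model has no practice effect, and repeat testing may raise scores, so the observed change could be positive.

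**The size is assumed.** Mean, SD and reliability are not in the documents, and over the main range the bias is within the sampling error of 20 patients. This stands, but sampling error does not remove bias from an estimate that is to be reused.

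**The sample is not shown to be unimpaired.** A reader might infer from Annex 6 that it is. Section 5.3 requires a classification of impairment as well as the score, and it does not invoke the annex's severity rows, which are one of several readings on a general interpretation sheet. What remains is conflicting wording.

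**MMSE is minor here.** The primary outcome is acceptability and usability, and the cognitive hypothesis concerns attention and memory, which have their own tests. This limits the weight of the point but does not remove it.

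**Conclusion.** The point holds in conditional form. The dual role of MMSE, the single scheduled pre-programme assessment, the uncontrolled test and the planned reuse of effect sizes are all in the documents. If the selection score is also the baseline, the entry rule pulls the expected change down. The direction of that pull is firm. Its size, about -0.02 to -0.84 points with no true effect, rests wholly on the assumed SD 2 to 3, clinic mean 23 to 27 and reliability 0.7 to 0.9, and leaves practice effects out. The limit on gains from the cap at 30 does not depend on which score decides entry.

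The tested MMSE change is therefore hard to interpret and unsuitable as a planning effect size. The main acceptability result is not affected. The mismatch between 5.3 and Annex 6 is a separate inconsistency for the investigators to resolve. This is worth correcting but does not threaten the pilot.

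**What to change.** - **5.4.1 and 5.7:** treat MMSE as an entry and descriptive variable. Report pre and post values and the number of patients at 30, without a p-value, and state that its change will not be used to size future studies.
- **General cognition:** let MoCA, already collected at both time points, carry the comparison. Note that it is not the entry variable but may inherit a weaker pull, since a good or bad day can shift both tests together.
- **5.8:** add regression to the mean and the MMSE ceiling to the limitations.
- **5.3 and Annex 6:** the investigators should reconcile the entry wording with the severity rows. No cut-off or definition is proposed here.

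The cost is protocol wording and one fewer tested secondary outcome. No extra visit or test is needed.

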threats of the use of virtual reality technology in cognitive rehabilitation and to optimize the usability of HCI in interventions that use this technology. Furthermore, a recent study conducted by Qiu et al. (2022) supports the acceptability and tolerance of a virtual reality-based cognitive training program in older adults, reflecting that the majority of participants found VR attractive and easy to use, without serious or severe adverse events.

The main objective of this project is to carry out a pilot study to clinically evaluate the effectiveness of virtual reality (VR) sessions in a selected group of 20 patients from the El Carme Socio-Health Center in Badalona. These VR sessions will consist of 360-degree immersive experiences, designed and provided by Reality Telling, that will focus on recreating familiar environments and implementing memory and attention training exercises.

The purpose of these sessions is twofold. On the one hand, we seek to validate the acceptability of these immersive experiences among patients and healthcare professionals, evaluating their willingness to adopt and interact with this innovative form of therapeutic intervention. On the other hand, we propose to examine the impact of immersive experiences in terms of improving cognitive performance, as well as on the commitment and motivation of patients towards their own cognitive rehabilitation process.

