3. HYPOTHESIS OR STUDY QUESTION

Main Hypothesis:

The application of a cognitive stimulation program with virtual reality will be well accepted by patients with mild cognitive impairment.

Secondary Hypotheses:

- Virtual reality interventions will be perceived as useful and motivating by patients, promoting positive adherence to the cognitive stimulation program.
- Patients will improve their cognitive performance (attention and memory) on cognitive scales after the sessions.
- Virtual reality interventions will be perceived as useful and applicable as a tool in the clinical practice of cognitive stimulation by healthcare professionals.

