5.6 Sample size

The sample size for this pilot study has been established at 20 patients. This decision is based on several factors:

Preliminary nature of the study: As this is a pilot study, the primary objective is to evaluate the usability and acceptability of the virtual reality intervention, rather than to demonstrate effectiveness. Pilot studies typically have smaller sample sizes than full studies.

Resources and capacity: The capacity of the El Carme Socio-Health Center in Badalona and the available resources (both in terms of staff and virtual reality equipment) also influence the sample size. Ensuring that each participant can receive appropriate care and support is

critical to accurate data collection and a positive patient experience.

Patient variability: Although the sample size is small, it is expected to reflect the diversity of the patient population in terms of severity of cognitive impairment, gender, age, etc. This diversity may provide a deeper understanding of how different types of patients may interact with virtual reality technology.

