7. PROTECTION OF PERSONS UNDER INVESTIGATION

7.1 Benefit-risk evaluation for research subjects

This interventional study uses virtual reality (VR) for cognitive stimulation of patients with cognitive impairment. The following potential risks and benefits to participants have been identified, along with specific mitigation strategies for the identified risks.

Risks and Mitigation Strategies:

1- Side effects of VR: Some patients may experience dizziness or disorientation with VR. To mitigate this risk, static or smooth motion VR experiences will be designed, and the technology will be introduced gradually. Side effects will be carefully monitored, especially in patients with conditions that may increase risk.

2- Patient acceptance: Since VR is a relatively new technology, it can be intimidating for some patients. To overcome this barrier, the potential benefits of VR will be effectively communicated and patient concerns will be proactively managed. Engagement with healthcare personnel during the process can improve patient acceptance and adherence.

3- Technical problems: Like any technology, VR can face technical problems such as hardware or software failures, or Internet connectivity problems. To mitigate this risk, backup equipment will be available and appropriate training will be provided to healthcare personnel to handle VR equipment. Fast and efficient technical support will also be guaranteed to resolve any issues that may arise.

4- Technical problems: Like any technology, VR can face technical problems such as hardware or software failures, or Internet connectivity problems. To mitigate this risk, backup equipment will be available and appropriate training will be provided to healthcare personnel to handle VR equipment. Fast and efficient technical support will also be guaranteed to resolve any issues that may arise.

5- Exclusion of certain patients: Some patients may not be able to participate due to severe cognitive impairment, dizziness, certain visual impairments or other health conditions, which could potentially lead to feelings of exclusion or frustration. To mitigate this risk, communication with patients about the limitations of who can participate in the study will be clear, explaining health and safety reasons. For those patients who are unable to participate, other alternative activities or interventions will be explored.

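### Acceptability is scored only in the 20 patients who agreed to try VR and refusals are not counted, so the scores alone cannot show acceptance among the centre's patients

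*Combined protocol and SAP*

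**What the plan says.** Section 1 (Background and justification) says the study will validate acceptability among patients and professionals by "evaluating their willingness to adopt and interact with this innovative form of therapeutic intervention". The main hypothesis in section 3 is that the programme "will be well accepted by patients with mild cognitive impairment". Section 4.1 gives the main objective as "To evaluate the acceptability of the cognitive stimulation program based on virtual reality among patients with mild or moderate cognitive impairment" at the El Carme centre; it does not limit this to patients who agree to take part.

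Section 5.3 excludes "Patients who are unable or unwilling to give informed consent". Under its sampling heading, qualifying patients "will be invited to participate until the desired number of participants is reached". Sections 5.2 and 5.6 set that number: "The sample size for this pilot study has been established at 20 patients".

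Section 5.4.1 measures acceptability and usability with a satisfaction questionnaire and the SUS after the eighth session. Section 5.7 summarises the SUS scores descriptively.

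**The concern.** Willingness to take up VR shows itself first when a patient is invited. In this plan a patient who declines at that moment leaves no trace. Read literally, 5.3 makes that patient ineligible, so uptake worked out later among protocol-eligible patients would be 100% by construction.

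The main question is whether VR is well accepted at this centre. If many patients declined because of VR, good scores from the remaining 20 would describe a self-selected group. If decliners would have been less favourable than participants, which is plausible but not documented, reading the scores as a result for the whole centre would flatter the programme. This matters for what follows: 5.1 foresees possible incorporation into the Day Hospital programme, and 5.7 says the results will inform future studies.

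**Working it through.** There is no plan figure to reproduce. The 20 in 5.6 rests on pilot status, resources and expected diversity, with no formula or precision target. The check is therefore whether any section records a denominator, and what its absence hides.

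**Where a count of invitations or refusals could appear**

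- 5.4.1 (outcomes): questionnaire, SUS and cognitive tests. No uptake or refusal.
- 5.4.2 (other variables): age, sex, etiology, schooling, other treatments. No refusal.
- 5.5 (visits): the selection visit covers consent, demographics and cognitive results. No log of patients approached.
- 5.7 (analysis): descriptive SUS, paired cognitive comparisons, correlation and regression. No denominator of invited or eligible patients.
- 6.1 (data sources): data come from participants. This section places the questionnaires after every session, whereas 5.4.1 places them after the eighth; the two need reconciling, but under either only participants are asked.
- 7.2 (consent): a record of the consent process is kept per participant, with no provision for those who decline.
- 5.8 (limitations): no control group, short duration, small sample, self-report. Selection by willingness is not named; the sample is instead expected to reflect the diversity of the patient population.

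**What the missing count hides**

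Inputs: number enrolled = 20 (5.2, 5.6). Number invited is not given; 25, 33 and 50 are assumed.

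Uptake = enrolled / invited, with a Wilson 95% interval:

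- 20/25 = 80% (61% to 91%)
- 20/33 = 61% (44% to 75%)
- 20/50 = 40% (28% to 54%)

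The planned result is a summary of the enrolled patients' SUS scores. The number invited does not enter it, so for the same 20 sets of answers the report would read identically in all three cases.

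The intervals are approximate. They treat the number invited as fixed, whereas under 5.3 the number consenting is fixed and the number invited varies. This has little numerical effect.

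**The case against.** Several points on the other side stand.

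- **The main outcome is post-use.** A reader might infer that the design selects on its own main outcome. The documents do not support that. Section 5.4.1 defines the outcome as questionnaire and SUS after use, and most Annex 7 items (weight of the glasses, dizziness, difficulty learning) can be answered only by users. Annex 7 also asks whether the patient would like to use the program often, so willingness is partly measured after exposure. Selection is on consent, which may correlate with the outcome but is not the outcome.
- **Consent is unavoidable.** Section 7.2 admits nobody without it. Rewording the exclusion changes nobody's enrolment; its only use is to keep decliners in the denominator.
- **Refusing the study is not the same as refusing VR.** Participation also involves two rounds of cognitive testing and data processing, and a legal representative may decide. It is therefore tempting, but wrong, to divide favourable ratings by the number invited and call the result acceptance of VR: that counts every refuser as rejecting VR. Nor does 5.7 define a favourable percentage that could be rescaled in this way.
- **Section 7.1 does not predict refusals.** It says "Since VR is a relatively new technology, it can be intimidating for some patients" and describes communication to manage this. That makes VR-related refusal plausible, no more.
- **The plan is modest.** It calls itself a pilot, labels the sampling non-probabilistic and concedes limited representativeness. But 5.8 attributes that to design and size, not to self-selection, and acceptability is this pilot's main objective.

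None of this supplies the missing count.

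**Conclusion.** The point holds as a limit on what the scores can show. The questionnaire and SUS results are valid for patients who agreed to try VR. Because invitations and refusals are not recorded, those results are compatible with high or low uptake and cannot alone support a conclusion that the programme is well accepted among the centre's patients.

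The size is unknown, since the documents give no number eligible, invited or refusing. The range of 80% down to 40% uptake follows from assumed invitation counts and is not a forecast.

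A reader might also infer that the main hypothesis could be declared confirmed while most patients refuse. The documents do not go that far: neither section 3 nor 5.7 gives a threshold for good acceptance, so there is no confirmation rule. That is a separate gap, which counting refusals would not close.

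This is an inexpensive improvement that bears on the main question. It does not invalidate the planned scores.

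**What to change.** - **5.3:** treat otherwise eligible patients who decline as eligible decliners. They are still not enrolled. Keep an anonymous tally of patients eligible, invited, consented and declined, with one reason category (VR-related, other, unknown) and a note when a legal representative decided.
- **5.4.1 and 5.7:** report uptake (consented / eligible invited, 95% CI) and the share of VR-related refusals beside the SUS and satisfaction scores, as a separate acceptability indicator not merged into the score.
- **5.7 and 5.8:** state that the scores apply to patients who agreed to try VR, and name self-selection as a limitation.

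The cost is a tally sheet during recruitment and a few extra figures in the report, with no extra patients, visits or identifiable data. The downsides are a possibly less favourable headline and some refusals that concern research rather than VR, which is why the reason is recorded. If recruitment is already over, the restricted claim still applies, and uptake should be reported only if the invitations can be reconstructed reliably.
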